Blood samples will be obtained serially in order to determine the immune response against the gp100(g209-2M) and MAGE-3 vaccines (weeks 0, 2, 4, 8, 12, 16, 20, and 24: weeks 8 and 16 will not be collected when leukapheresis is performed; blood samples will be collected by leukapheresis at weeks 0 and 8 (+/- 1 week), and 16 when feasible). To evaluate the inflammatory infiltrate at the site of immunization, biopsies will be obtained of vaccination sites as outlined in section 7.3

Subjects in the adjuvant cohort.

Vaccination will continue for the designated 8 weeks. Blood draw and pheresis times will be the same as subjects in the metastatic disease cohorts. Subjects will be monitored for disease recurrence, but if recurrence occurs prior to the completion of blood draws or pheresis these tests can still be obtained if deemed valid by the PI.

Subjects in the metastatic disease cohort:

At the end of 8 weeks, we will allow tumor progression since patients will have only received vaccine at this point. We estimate that of a total of approximately 24 patients in this cohort, 17% will drop off at this point, leaving a total of 20 patients to be treated in Part 2. To have enough patients to evaluate the secondary endpoints, 20 additional patients may be enrolled in the metastatic disease cohort so that at least 30 patients (10/arm) with gel and 10 are available for Part 2.

At the end of 8 weeks of vaccine, cutaneous lesions (at least 2 and up to 10 lesions) will be assigned by the physician according to region to receive or not to receive 0.2% R848 gel. The CORe randomization system will not be used in Part 2. The physician will designate the regions and which tumors will be treated. The area of cutaneous lesions will be divided into two regions, Region A and Region B, striving to equalize tumor burden in each designated region as best as possible. When feasible, Region A will be a proximal group of lesions, and B distal. When this proximal – distal differentiation is not feasible because of the characteristics of the metastatic pattern, then A and B will be assigned to regions in no particular order. If the two regions coalesce during the vaccination phase, the coalesced tumor may be divided into two regions. Each target tumor whether it is treated or untreated will be marked, measured and photographed for the medical record. Because this dose provides the highest level of immune cell

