infiltration, we plan to utilize this dose of R848 two times per week every 3-4 days (+/- 2 days), with the option of dose reducing from twice to once a week should patients experience any grade 3 or greater toxicity.

The physician will designate which of the two regions to receive or not to receive R848. (For example, if the cutaneous disease is limited to the thigh, the area of lesions will be divided in two with one region proximal and one region distal. Then the proximal region is assigned region A and the distal assigned region B. Resiquimod to be applied to region A or B. A 5mm margin will be included in the treatment area around each of the lesions at a spread rate of 10mcg/cm^2. The sum of the area of all treated lesions will not exceed 100cm^2. The treatment area will be allowed to air dry for 30 minutes and then covered with a gauze dressing which can be removed the following day. The R848 gel will be applied in the clinic by the research nurse for the first two weeks of administration, and then the subject will apply the gel at home thereafter. The patient will be trained for gel self-administration by the research staff. Sachets of gel will be supplied for home use and the subject will be instructed on maintaining a home record of administration. This home record or a progress note by one of the research team reviewing home administration may each act as a source document for all matters regarding home administration during this period. The gel may be applied in the clinic for longer than the first two weeks at the discretion of the investigators.

Tumor biopsies of treated and untreated lesions will be obtained as outlined in section 7.3 when feasible in order to assess T-cell infiltration and function at the site.

In order to give patients the opportunity to receive R848 gel on all their lesions, we will allow cross-over of patients who do not respond in untreated lesions by week 16 (8weeks after initiating gel on the tumors) in the untreated lesions to receive R848 gel on all of the lesions, but these patients will not be included in the final analysis of clinical endpoints that occur following week 24. Patients will not cross-over until after all blood, biopsies, and data are recovered for assessment of the primary endpoints in any subject. Treatment with R848 gel will continue for up to 4 months beyond week 24 as long as there is no disease progression.

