#### **9.6 Baseline measurement**

In this trial a period of immunization opens the treatment, and immunization alone mediates tumor response rarely. (Cancer immunotherapy: moving beyond current vaccines. Rosenberg SA, Yang JC, Restifo NP. *Nat Med.* 2004 Sep;10(9):909-15.) So with this sequence, as has been seen with other immunologic mediators, we should expect that a period of progression may precede any response from the treatment.

Therefore, because subjects are likely to progress during the vaccination portion of the study, the baseline will be that measurement during the first 10 weeks of the study at which the tumors are at their maximum size (based on sum of LD). Progression will be allowed during these first 10 weeks without withdrawal of the subject from treatment or from the study. This includes increase in the size of the lesions as well as the appearance of new lesions.

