## 11.0 Statistical Considerations

### Overview

This is a randomized phase II trial enrolling melanoma patients who are HLA-A2+ with or without HLA-DP4+. Patients of two separate types will be enrolled in separate cohorts. One cohort includes patients who are NED but at high risk for recurrence. The second cohort will include patients with non-visceral metastatic disease and must have at least two evaluable and biopsiable lesions to be eligible for the trial.

The trial will have two parts. In Part 1 (both cohorts), we will fairly randomize patients to receive either the gp100(g209-2M) +/-MAGE3 peptide vaccine plus a topical TLR 7 /8 agonist, R848, (Arm A) or the gp100(g209-2M) +/- MAGE3 vaccine alone Arm B). The randomization will be stratified by cohort. A total of 48 patients will be enrolled, 24 per arm. All patients will receive the gp100(g209-2M) vaccine (those who are HLA-DP4 + will also receive the MAGE3 vaccine) weekly (for 8 weeks) and the patients randomized to receive R848 gel will have the gel applied to the gp100(g209-2M) vaccine site weekly.

After 8 weeks of treatment on Part 1, Part 2 of the trial begins. In Part 2 (only patients in the metastatic disease cohort), the treating physician will divide the area of cutaneous lesions into regions, Region A and Region B and designate the two regions to receive or not to receive R848. At least one lesion will be randomly assigned to receive R848 from weeks 8 through 24, and one will not. One lesion from each region will be chosen for biopsy as outlined in section 7.3. If a patient has more than two evaluable lesions, we will stratify by lesion size to assure that the lesions will be comparable.

As a safety measure, if a patient's untreated lesions grow while treated lesions are stable or shrink, all lesions will be treated with R848. This will occur after the assessment of the primary endpoints of the study, so it will not affect the analysis of these endpoints.

In April 2015, the trial is being further modified to add an additional 20 patients with metastatic disease, all of whom will receive the the gp100(g209-2M) +/-MAGE3 peptide vaccine plus R848 (Arm C). These patients will not be part of the primary comparative study analysis of T-cell responses in the blood. The purpose of these patients is to provide additional information on characterizing tumor response, defined as at least a 50% shrinkage in tumor size by irRC criteria.

### Part 1

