The primary outcomes for part 2 of the trial are immune cell infiltration for pDCs, mDCs, and NK cells in the tumor biopsy samples. This can be assessed in the metastatic disease cohort only, since those subjects in the adjuvant therapy cohort are free of disease. Tumor samples will be taken as outlined in section 7.3. Three different types of analyses will be performed on these tumor biopsies: (1) Immunohistochemistry (IHC) for the degree of pDC, mDC, and NK cell infiltration, (2) Flow cytometry (FACS) analysis for infiltrating melanoma specific CD8+ T cells, and (3) Quantitative RT-PCR (qRT-PCR) assays for IFN- $\gamma$ , IFN- $\alpha$  (and other type I interferons), IL-12, and TGF- $\beta$ . For each of these outcomes, we will determine the differences in each of these parameters between the pretreatment and post-treatment samples for each of the biopsied lesions for each patient. Mixed-effect models will be fit for each parameter to assess the effects of treatment, time, and the initial randomization to gp100(g209-2M) +/- MAGE-3 vs. gp100(g209-2M) +/- MAGE-3 +R848. If there is no evidence of an effect due to the initial randomization in Part 1, the changes from baseline for the R848 treated lesion and the untreated lesion will be calculated, and these differences will be compared between the R848 and non-R848 lesions by using a paired t-test.

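### Part 2 says both that the physician chooses the R848 region and that a lesion is assigned at random, so the within-patient lesion comparisons lack the protection of chance allocation and cannot carry a causal reading

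*Combined protocol and SAP*

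**What the plan says.** Section 6.0 (metastatic disease cohort) takes Part 2 out of the randomization system: "The CORe randomization system will not be used in Part 2. The physician will designate the regions and which tumors will be treated". It then repeats: "The physician will designate which of the two regions to receive or not to receive R848". The choice is made after the 8 weeks of vaccine.

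Section 11.0, Overview, has the treating physician split the lesions into two regions and "designate the two regions to receive or not to receive R848". The next sentence reads: "At least one lesion will be randomly assigned to receive R848 from weeks 8 through 24, and one will not". No list, system, ratio or concealment is described for that assignment. Section 7.3 also speaks of random selection, but that concerns which tumor is biopsied, not which receives gel.

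The treated-versus-untreated contrast is used in several analyses in Section 11.0:
- Part 2: mixed models for the biopsy outcomes, including pDC, mDC and NK infiltration (called primary for Part 2). If the initial randomization shows no effect, "these differences will be compared between the R848 and non-R848 lesions by using a paired t-test".
- Secondary endpoints: a mixed model for inflammation and adhesion molecules in treated and untreated tumors.
- Secondary endpoints: McNemar's test on lesion response. The text says that significance shows whether the cream improves outcome.
- On the likely reading, also the Wilcoxon signed rank test between lesions and the mixed model for immune-cell infiltration into tumor.

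**The concern.** Two current statements describe the allocation differently, so two analysts could report the same data as randomized or as not randomized. If the physician chooses, nothing in the design makes the treated and untreated regions exchangeable. A test's nominal type I error then no longer describes the chance of a false claim about the gel.

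For lesion response the documents show a possible route. Designation follows a vaccination phase in which tumors are expected to change; Section 9.6 sets its baseline rule "because subjects are likely to progress during the vaccination portion of the study". The physician can thus see how each lesion has behaved before choosing. Regions of equal burden at week 8 need not be growing equally fast. Where the proximal/distal split is used, a habit of treating one side would also tie location to treatment.

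For the biopsy outcomes the documents name no such route, so bias there is possible but not shown.

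The stakes are the Part 2 primary outcomes and the lesion-response comparison. Tumor-site effects are secondary objectives in Section 1.2.

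**Working it through.** **1. The plan's own Part 2 figure.** Section 11.0 expects 24 metastatic patients and 17% drop-off: 24 × 0.83 = 19.9, so 20 (10 per arm). For a one-sided 5% two-sample t-test at 1.2 SD (noncentral t), 9 per arm give 78.5% power and 10 per arm 82.5%. The stated 20 patients for 80% power is reproduced. It does not depend on how lesions are allocated, and it is not a calculation for the paired lesion contrast.

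**2. Allocation statements side by side.**

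| Place | Who or what decides the treated region |
|---|---|
| Section 6.0, first statement | Physician; CORe not used |
| Section 6.0, second statement | Physician |
| Section 11.0 Overview, one sentence | Treating physician |
| Section 11.0 Overview, next sentence | Random assignment, no mechanism |

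No other section resolves this.

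**3. Paired t-test, illustration.** The documents give no imbalance figure. Assume that R848 has no effect and that selection shifts the within-patient difference by δ SD of that difference, in the same direction across patients. The chance of a result in favour of gel is P(T > t₀.₉₅,ₙ₋₁), where T is noncentral t with n − 1 df and noncentrality δ√n.

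| Pairs | δ | δ√n | Critical t | Rejects in favour of gel |
|---|---|---|---|---|
| 20 | 0 | 0 | 1.729 | 5.0% |
| 20 | 0.2 | 0.894 | 1.729 | 21.7% |
| 20 | −0.2 | −0.894 | 1.729 | 0.6% |
| 40 | 0.2 | 1.265 | 1.685 | 34.4% |

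The plan gives no sidedness for this test. At two-sided 5% with 20 pairs and δ = 0.2 the rate in favour of gel is 13%. Twenty is the original Part 2 number. Forty is my reading of Section 6.0 after the expansion (30 with gel plus 10).

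**4. McNemar's test, illustration.** Section 11.0 puts response under standard of care at no more than 5%. Assume 5% in each region, independently: discordance = 2 × 0.05 × 0.95 = 9.5%. The number of discordant patients is D ~ Bin(n, 0.095). Given D, the number favouring gel is Bin(D, s), where s is the split caused by selection alone. The exact two-sided 5% test needs at least 6 discordant patients, all one way (2 × 0.5⁶ = 0.031; with 5 it is 0.0625). The nominal rate in favour of gel is 2.5%.

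| n | Split s | Exact test, in favour of gel |
|---|---|---|
| 20 | 70:30 | 0.1% |
| 20 | 100:0 | 0.9% |
| 40 | 70:30 | 1.8% |
| 40 | 80:20 | 4.3% |

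The plan does not say which version it will use. The uncorrected chi-square version at 70:30 gives 2.5% (n = 20) and 9.8% (n = 40). At an assumed 30% discordance the exact test with n = 20 and 70:30 gives 6.3%, but that discordance does not fit response rates of 5% or less.

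**The case against.** The strongest defence is that the plan is open about not using CORe and builds in several safeguards:
- tumor burden is balanced between regions, and lesions are stratified by size when there are more than two;
- biopsied tumors are selected at random, and biopsy outcomes are analysed as change from baseline;
- target tumors are marked, measured and photographed;
- the response baseline is the maximum size in the first 10 weeks, response needs 50% shrinkage, and it must be confirmed at least four weeks later.

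Pairing removes differences between patients, and choices that differ in direction between patients would tend to cancel. All of this stands and makes a large bias less likely. None of it makes the treated region a chance selection with respect to growth rate, depth or site.

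It is also fair that two of the listed tests are uncertain cases. The signed rank sentence closes a paragraph that is mainly about the vaccine site, and the infiltration model refers to treatment groups on the blood-draw schedule. I count them as lesion contrasts on the likely reading only.

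A reader might infer that the Part 2 results are biased toward R848, or that false positives of 22% or 34% are to be expected. The documents do not support that: those figures rest on an assumed shift in one direction, for biopsy outcomes where no route to bias is shown. An opposite shift would hide a true effect. A reader might also infer that the trial's main result is in doubt. It is not, because Part 1 is randomized through CORe.

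**Conclusion.** The contradiction is certain. Given physician choice, it follows that the lesion contrasts are not protected by chance allocation and that the causal reading of McNemar's test is unsupported. The amount of bias is unknown in size and direction. Under the stated assumptions it could be material for the paired t-test and is small for the exact McNemar test, unless the split is extreme, the chi-square version is used or discordance is much higher than the plan's response rates suggest.

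Not affected: the Part 1 arm comparison, the antigen-spreading model (not a lesion contrast) and the Arm A plus C response test against 5%.

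This should be fixed, but it does not threaten the primary objective.

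**What to change.** 1. **Patients not yet assigned.** The physician marks and records two regions of similar burden, each compatible with the plan's existing area limit ("The sum of the area of all treated lesions will not exceed" the figure given in Section 6.0). The treated region is then drawn 1:1 at random, by CORe or from a pre-generated concealed list. Analyse as drawn. Log any exception and leave it out in a sensitivity analysis.
2. **Patients already assigned, or all Part 2 patients if randomization is not adopted.** Delete the random-assignment sentence in the Section 11.0 Overview, label the lesion contrasts non-randomized and remove the causal sentence on McNemar's test. Report these patients separately from randomized ones. A main effect for allocation method would not be enough, because it is constant within a patient.
3. **One rule.** Reconcile Sections 6.0 and 11.0 to a single allocation rule.
4. **Measurement.** Section 9.5 has the treating physicians measure tumors, and they can know which lesions were treated. State this as a separate limitation of the McNemar comparison; random allocation does not solve it.

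**Cost.** One allocation step per patient and an amendment, with no extra visits. The physician loses the choice of region, and lesions already assigned cannot be repaired. The documents do not show how many patients remain unassigned.

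If the change starts with the 20 Arm C patients, about 20 × 0.83 = 16.6 pairs would remain. This applies to them the drop-off estimated for the original cohort ("We estimate that of a total of approximately 24 patients in this cohort, 17% will drop off at this point"); optional biopsies could reduce the number further. Allocation method would then coincide with Arm C. Since every Arm C patient receives vaccine plus R848, that subset could not estimate the Part 1 randomization term in the Part 2 models or check the condition for the paired t-test. The plan should say so.

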#### **9.5 Immune-Related Best Overall Response Using irRC (irBOR)**

irBOR is the best confirmed irRC overall response over the study as a whole, recorded between the date of first dose until the last tumor assessment before subsequent therapy (except for local palliative radiotherapy for painful bone lesions) for the individual subjects in the study. For assessment of irBOR, all available assessments per subject are considered.

If a lesion is surgically resected or treated with definitive radiosurgery, the size of the lesion prior to the definitive local therapy will be included in the calculated irBOR.

Primary evidence of antineoplastic activity will be evaluated as a function of objective tumor response following the vaccination period. An overall objective assessment of all measurable and non-measurable disease will be performed as outlined in 9.1. Tumor assessments should be performed by physical exam, ultrasound, MRI or CT scan, throughout the study. The treating physicians will perform tumor measurement.

Radiological studies must account for all lesions that were present at baseline and must use the same techniques as used at baseline. All

complete and partial responses must be confirmed by a second assessment at least four weeks later.

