### **Additional Cohort of Non-Randomized Patients**

As noted above in the Overview, after the initial 48 patients have been enrolled in the randomized portion of the trial, 20 additional patients with metastatic disease will be enrolled into Arm C in order to further characterize tumor response of R848. These patients will not be included in the primary analysis. Tumor response as measured by a 50% shrinkage in tumor size by irRC criteria will be the primary endpoint for these patients. The response rate associated with the standard of care in these patients is no more than 5%. We expect a total of 10 metastatic disease patients in Arm A from the initial randomized portion of the trial. Combined with the additional 20 patients (Arm A and C, with a total of 30 patients, we will have 82% power to detect an increase to 22%, assuming a one-sided exact binomial test with a 5% Type I error rate.

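### Leaving cross-over patients out of clinical endpoints after week 24 makes the analysed set depend on a post-baseline tumour outcome and leaves the denominator of the 30-patient response test open

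*Combined protocol and SAP*

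**What the plan says.** Section 6.0 (Treatment Plan), metastatic cohort: "we will allow cross-over of patients who do not respond in untreated lesions by week 16", so that all their lesions can then be treated. The same sentence adds that "these patients will not be included in the final analysis of clinical endpoints that occur following week 24". Two further statements bear on timing: "Patients will not cross-over until after all blood, biopsies, and data are recovered for assessment of the primary endpoints in any subject", and "Treatment with R848 gel will continue for up to 4 months beyond week 24 as long as there is no disease progression".

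The Overview in section 11.0 describes the switch differently: "if a patient's untreated lesions grow while treated lesions are stable or shrink, all lesions will be treated with R848". It adds that this comes after the primary endpoints have been assessed and so does not affect them.

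Section 11.0, Additional Cohort of Non-Randomized Patients, says of Arm C: "Tumor response as measured by a 50% shrinkage in tumor size by irRC criteria will be the primary endpoint for these patients". The test combines 10 expected Arm A patients with the 20 in Arm C: "with a total of 30 patients, we will have 82% power to detect an increase to 22" per cent. It is a one-sided exact binomial test at 5% against a standard-of-care rate of at most 5%. That section gives no time window and mentions no exclusion.

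Section 9.5 defines best overall response over the whole study: "For assessment of irBOR, all available assessments per subject are considered". It also requires complete and partial responses to be confirmed at least four weeks later. Section 1.2 lists objective response rate and progression-free survival (PFS) as secondary objectives.

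**The concern.** Cross-over is decided by what untreated lesions have done by week 16, and cross-over then decides whether the patient is analysed for later clinical endpoints. Selection therefore acts on a variable closely related to the endpoint.

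The endpoints are still being read after week 24. Section 11.0 schedules response assessment at weeks 8, 16 and every 8 weeks after that, and gel may continue for up to 4 months past week 24. A response first seen at week 24 can be confirmed no earlier than week 28.

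The sections also give no single rule for who is counted. Section 6.0 removes cross-over patients after week 24. Section 11.0 plans on all 30. Section 9.5 uses every assessment and sets no cut-off. The clause protecting the primary endpoints does not settle this, because response is itself the primary endpoint for Arm C and has no stated closing date. A single-arm test against a fixed 5% depends entirely on its numerator and denominator. If both are open, they can be settled after the results are known.

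**Working it through.** **Inputs from the plan.** n = 30 (10 Arm A + 20 Arm C), null rate 5%, alternative 22%, one-sided exact binomial test at 5%, stated power 82%. The documents give no cross-over rate, so every share excluded below is an assumption, shown as a range.

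**Step 1: the plan's own figure.** The test rejects at the smallest r for which P(X ≥ r | n, 0.05) ≤ 0.05.
- P(X ≥ 4 | 30, 0.05) = 0.0608, too large.
- P(X ≥ 5 | 30, 0.05) = 0.0156, so r = 5.
- Power = P(X ≥ 5 | 30, 0.22) = 0.821, which reproduces the stated 82%.

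**Step 2: cross-over patients removed from the denominator.** A small change is enough to turn the result:
- 4/30: p = 0.0608, negative.
- 4/28, after two non-responders are dropped: p = 0.0491, positive.

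Now suppose all responders stay and each non-responder is dropped independently with probability q. The expected observed rate is approximately p / [p + (1 − p)(1 − q)]. The chance of a positive result comes from re-running the exact test on each reduced denominator and summing over the possible counts. At a true rate of 5%:

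| q (assumed) | Expected observed rate | Chance of a false positive |
|---|---|---|
| 0 | 5.0% | 1.6% |
| 0.25 | 0.05 / (0.05 + 0.95 × 0.75) = 6.6% | 6.1% |
| 0.50 | 0.05 / (0.05 + 0.95 × 0.50) = 9.5% | 12.4% |
| 0.75 | 0.05 / (0.05 + 0.95 × 0.25) = 17.4% | 25.6% |

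**Step 3: some responders also cross over and are dropped.** Let s be the share of eventual responders dropped. The expected rate becomes p(1 − s) / [p(1 − s) + (1 − p)(1 − q)], which exceeds p only when q > s. At a true 22%:
- s = 0.25, q = 0.5: 29.7%.
- s = q = 0.5: 22%, no bias.
- s = 0.5, q = 0.25: 15.8%, a downward bias.

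**Step 4: patients kept, late responses not counted.** If a share l of all responses comes after week 24 in cross-over patients and is ignored, the observed rate is 0.22(1 − l). With l = 0.25 assumed:
- Rate = 0.22 × 0.75 = 16.5%.
- Power = P(X ≥ 5 | 30, 0.165) = 0.566.
- At a true 5%, the false-positive chance falls to 0.5%.

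**Step 5: can a cross-over patient be an overall responder?** Section 6.0 aims at equal tumour burden in the two regions, and section 9.4 sets partial response at a 50% fall in the summed products over index and new measurable lesions. Assuming equal burdens, all index lesions in the two regions and no new lesions, the overall fall is 0.5t + 0.5u, where t and u are the falls in treated and untreated lesions.
- u = 0 needs t = 100%.
- u = 40%, still short of response, needs t = 60%, since 0.5 × 60% + 0.5 × 40% = 50%.

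So such a patient can be an overall responder, but only if the treated lesions do much better than the untreated ones.

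**The case against.** The strongest objection is that the direction of bias is not fixed. The exclusion refers to endpoints occurring after week 24, so it can be read as leaving late events uncounted while the patient stays in as a non-responder. Step 4 shows that the bias is then downward. The trigger in section 6.0 also looks only at untreated lesions, and the trigger in the Overview picks out patients whose treated lesions are holding or shrinking. Dropping such patients can hurt R848: 5/30 (p = 0.016) less two responders and six non-responders is 3/22 (p = 0.095). All of this stands. A reader might infer that the rule must inflate the response rate, or that either reading favours R848. The documents do not support either inference.

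A reader might also infer that the patients lost from PFS are the ones doing badly. That is not established. Section 10.1 takes patients with progressive disease off treatment after the first 10 weeks, so those who cross over are largely patients without overall progression. Section 11.0 specifies no PFS analysis and nowhere says that patients are censored at cross-over. What remains is that inclusion in PFS after week 24 depends on outcome; the direction is unknown.

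For McNemar's comparison of treated and untreated lesions, exclusion after week 24 would, if anything, work against R848, because it removes pairs in which only the treated lesions responded.

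It can also be said that section 9.5 defines best response per subject, not the analysed population, and that section 11.0 does not itself apply the exclusion to its 30 patients. That is right. But section 6.0 does state the exclusion, for clinical endpoints generally, and nothing says it stops short of the response test.

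**Conclusion.** The point holds in a limited form. Section 6.0 makes the analysed set for clinical endpoints after week 24 depend on a post-baseline tumour outcome, and this is not reconciled with the response test in section 11.0 or the definition in section 9.5.

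Removing patients from the denominator makes inflation of the Arm A plus C rate likely but not certain. The 6% to 26% range for the false-positive chance rests on an assumed drop probability of 0.25 to 0.75 and on no responder being dropped. Leaving only late responses uncounted biases the rate downward; the 57% power assumes that a quarter of responses are lost this way. One sentence thus permits analyses that err in opposite directions.

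On the literal wording, the Part 1 T-cell endpoint, the week-12 biopsies, the regression on best response within 16 weeks and responses confirmed by week 24 are not affected. Severity: should be fixed before analysis.

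**What to change.** 1. Delete the exclusion of cross-over patients from section 6.0.
2. State in section 11.0 that every Arm A and Arm C metastatic patient stays in the 30-patient response denominator, and every metastatic patient in the PFS analysis, whether or not they cross over.
3. Fix in advance which best response is the main one: from all assessments, as in section 9.5, or from assessments before cross-over. Either is defensible: the first follows section 9.5, while the second avoids crediting responses to treatment of all lesions. Report the other as a sensitivity analysis, and show separately the responses first seen after cross-over.
4. Limit only the treated-versus-untreated lesion comparison to assessments before cross-over, since that is the contrast cross-over removes.
5. Reconcile the two descriptions of cross-over in section 6.0 and the section 11.0 Overview. Which clinical rule applies is for the sponsor and the investigator.

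The cost is wording in sections 6.0 and 11.0, with no added patients or visits. Keeping all 30 in the denominator retains the plan's own test (reject at 5/30, type I error 0.0156); its 82% power still refers to a 22% rate under whichever response definition is chosen as main. The downside is that the reported response rate may be less favourable.
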